### 4.1.1 Imputation Rules

#### 4.1.1.1 Imputation of the primary and key secondary efficacy endpoints

The imputation will be performed for participants’: mean weekly NRS scores, mean scores of each WOMAC subscale and PGA score.

## Single imputation

Single imputation will be used for tabulation of the primary and key secondary endpoints as well as ANCOVA analysis of primary and key secondary endpoints. In this case the missing or unevaluable data at Week 12 will be imputed using:

- A single imputation method LOCF or BOCF as specified in [Table 2](#) for tabulation only.
- A single LOCF imputation method for ANCOVA supplementary analysis and tabulation.

## Multiple imputation

Generally, it will be assumed that missing observations for the primary and key secondary endpoints are missing at random. The exception are observations that are missing due to lack of efficacy or an AE, also values that are invaluable or missing due to taking prohibited pain medication or excessive use of permitted rescue medication as presented in [Table 2](#). Those observations are assumed to be missing not at random (MNAR). Consequently, the pattern mixture framework (Ratitch B. and O’Kelly M., 2011) will be implemented by multiple imputation using steps summarized below, where 100 imputed datasets will be created across which the Rubin’s rule will be applied to combine the estimates. Execution details are provided in [Appendix B1](#). However, prior to executing the below steps, missing baseline of the primary and key secondary endpoints will be imputed using the SAS PROC MI statement MONOTONE REG with seed number =568000003 with number of iterations set to 100. KL grade as reported by Bioclinica also referred to as Clario will be included in the imputation model.

### *Step 1: Intermediate missing data imputation*

The non-monotone missing values will be imputed using the Markov chain Monte Carlo method assuming MAR and multivariate normality. This step will be executed using the SAS procedure PROC MI with the MCMC option with seed number=568000003 and number of iterations set to 1 and number of burn-in iterations fixed at 200. The treatment and Kellgren and Lawrence (KL) grade variables will be included in the imputation model.

### *Step 2: Imputation of missing patterns*

The missing/unevaluable values of each pattern that are defined by the intercurrent events as specified in [Table 2](#) will be imputed via the sequential regression method using the SAS PROC MI statement MONOTONE REG with seed number =568000003 as follows:

- MAR -The missing/unevaluable week 12 values of primary and key secondary endpoints will be estimated from the observed and imputed data from step 1

using the sequential modelling approach. That is, prior outcomes of the primary or key secondary endpoints at each visit will be considered for imputing missing week 12 values under the MAR assumption. In addition, the treatment and KL grade variables will be included in the model.

- **MNAR** – The missing/unevaluable week 12 values of primary and key secondary endpoints will be estimated from the observed and imputed data from step 1 using the baseline observation carried forward approach. Non-missing baseline records from participants from both the placebo and active treatment arms will be used to impute post-discontinuation records from both the placebo and active treatment arms with KL grade included in the model.

### *Step 3: Combining the imputed outcomes and Statistical analyses*

The imputed data from first two steps along with observed data will be analysed using the MCP-Mod and analysis of covariance (ANCOVA) model as described in section [4.2](#)

#### **MCP-Mod**

The estimated dose response parameters ( $\hat{\mu}^{(q)}$ ) with their covariance matrices ( $\hat{S}^{(q)}$ ) from each imputed dataset  $q = 1, \dots, Q$  obtained from ANCOVA model as specified in section [4.2](#) will be combined using Rubin's rule (as elaborated by Shomaker and Heumann, 2014). For more information refer to [Appendix C](#).

Dose-response model will be selected using the estimates combined above.

#### **ANCOVA**

The estimates obtained from the ANCOVA models will be combined using the MIANALYZE SAS procedure with adjusted degrees of freedom (EDF = option) based on the Rubin's method (Barnard and Rubin 1999).

In addition to the above, the missing Week 12 WOMAC pain subscale scores will be multiply imputed using sampling from a normal distribution approach ([Appendix B2](#)) depending on the reason for missing data as follows:

- *Discontinuation due to lack of efficacy or an AE or death:*  
Sampling from normal distribution with mean of participant's baseline score and standard deviation of the observed WOMAC pain subscale scores at Week 12 over all participants in FAS regardless of treatment assignment.
- *Missing data due to reasons other than those stated above:*  
Sampling from normal distribution with mean of participant's last available score and standard deviation of the observed WOMAC pain subscale scores at

Week 12 over all participants in FAS regardless of treatment assignment. It is possible that participant's last available score would be baseline score, in which case this score would be used.

Missing baseline of WOMAC pain subscale score will be also imputed using the same approach of imputing missing baseline of primary and key secondary endpoints described in the first paragraph of the multiple imputation section above. In addition, this MI with seed number =568000003 will also generate 100 imputed datasets. Each imputed dataset will be used for ANCOVA analysis, and its estimates combined using the MIANALYZE SAS procedure with adjusted degrees of freedom (EDF = option) based on the Rubin's method (Barnard and Rubin 1999).

#### **4.1.1.2 Imputation of other study variables**

Age at randomization will be derived for analysis purpose from the date of birth (DM module) and the randomization date (IE1 module) on the eCRF at screening as: year (randomization date) – year (date of birth), -1 if “day and month” of the randomization date is before “day and month” of the date of birth.

Participants with a partial date of birth (i.e., for those countries where year of birth only is given due to local regulatory constraints) will have an assumed date of birth of 1st Jan ([given year]).

Unless otherwise specified, safety assessment values of the form of “< x” (i.e. below the lower limit of quantification) or “> x” (i.e. above the upper limit of quantification) will be imputed as “x” in the calculation of summary statistics but displayed as “< x” or “> x” in the listings.

Adverse events: all AEs will be considered as treatment-emergent unless the opposite can be clearly stated. Imputation will be done only in the context of identifying TEAEs.

Medications/therapies: all medications will be considered as concomitant unless the opposite can be clearly stated.

Additionally, AEs that have missing causality (after data querying) will be assumed to be related to study treatment.

#### **4.1.1.3 Handling of missing/incomplete dates**

The original incomplete or missing dates will be presented in the listings.

In practice, partial AE or medication start dates will be imputed as follows:

- Missing day: Impute the 1st of the month unless month is same as month of first dose of study drug then impute first dose date. If the onset is before the first dose of study drug then impute with date of informed consent

- Missing day and month: impute 1st January unless year is the same as first dose date then impute first dose date
- Completely missing – impute first dose date unless the end date suggests it could have started prior to this in which case impute the 1st January of the same year as the end date

When imputing a start date, ensure that the new imputed date is sensible i.e., is prior to the end date of the AE or medication.

Partial AE or medication end dates will be imputed as follows:

- Missing day: impute day as the earlier of either the end date of the study or the last day of the month
- Missing day and month: as the earlier of either the end date of the study or the last day of the year
- Completely missing: if the event is not ongoing then input as the date of the last visit unless the start date is prior to first dose date in which case this date would be used for imputation

The same logic presented above will be used to impute partial dates of the start of the OA in order to derive the duration of OA based on the available date parts.

If a participant is known to have died where only a partial death date is available, then the date of death will be imputed as the latest of the last date known to be alive +1 from the database and the death date using the available information provided:

- For missing day only – using the 1st of the month
- For missing day and month – using the 1st of January
- For missing year – the analysis date will not be imputed

No other imputation will be made.

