#### 3.6.1 Adverse events

AEs and serious AEs (SAEs) as defined in the protocol appendix C will be collected from the screening, throughout the study, and including the follow-up period. The Medical Dictionary for Regulatory Activities (MedDRA) will be used to code the AEs, using the latest version. AEs will be graded according to the Common Terminology Criteria for AEs (CTCAE version 5).

A treatment emergent adverse event (TEAE) is defined as:

- any AE with an onset at the time of or following the start of study treatment through the end of study participation as per DS page in eCRF;

- any AE starting prior to the start of study treatment administration but increasing in severity at the time of, or following, the start of study treatment through end of study participation as per DS page in eCRF.

Any AE occurring before the first dose of study treatment and without worsening after the first dose will be included in the data listings but will not be included in the AE summary tables.

The causal relationship between IP and each AE will be recorded. For SAEs, causal relationship will be assessed for other medication and study procedures.

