##### **4.2.6.1 Adverse Events**

Summary tables will include TEAEs as defined in section 3.6.1, unless otherwise specified.

An AE overview summary table will be produced showing the number (%) of participants with at least one AE in each of the following categories:

- Any AE
- Any AE with an outcome of death
- Any SAE

- Any AE leading to discontinuation of study treatment
- Any severe AE
- Any AESI
- Any AE leading to withdrawal from study

For all categories above, the number (%) of participants with at least one causally related AE in that category will also be provided.

An additional table will be produced showing the incidence of participants with the following type of adjudicated events:

- RPOA (type 1 and 2)
- SIF
- Primary osteonecrosis,
- Pathological fracture

The number of participants treated per treatment group will be used as the denominator to calculate percentages.

Summary tables will be produced by MedDRA SOC and PT for the following categories:

- AEs
  - By age group as defined in section 4.2.8
  - By sex
  - By periods as defined in section 3.1.6.
  - By ADA categories as defined in section 3.4.2
- Severe AEs
- By periods as defined in section 3.1.6. Causally related AEs and SAEs
  - By periods as defined in section 3.1.6.
- SAEs with outcome death
- SAEs
  - By periods as defined in section 3.1.6.
  - By ADA categories as defined in section 3.4.2
- AEs leading to discontinuation of study treatment
- AESIs
  - By periods as defined in section 3.1.6
  - Separate table to be provided for each AESI category as defined in section 3.6.1.1
    - By periods as defined in section 3.1.6
    - Joint related AESI table by study periods will also include the exposure adjusted rates, where AE event rate (per 100 participant years) is defined as the number of

participants with that AE divided by the total number of days at risk for AEs across all participants in given treatment arm and multiplied by  $365.25 \times 100$  to present in terms of per 100 participant years.

- Most common non-serious AEs defined as AEs occurring in at least 5% of participants overall (in total column). For each SOC/PT, the number (%) of participants reporting at least one event at each level of summarisation will be presented. Participants with multiple occurrences of the same AE, the event will only be counted once per SOC/PT. Those will be sorted by international order for system organ class and in alphabetical order for preferred term.

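### For an adverse event with no start date, SAP Section 4.1.1.3 abandons the first-dose default on a weaker test than Section 4.1.1.2 requires, and the calendar year of the end date then decides TEAE status

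*SAP*

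**What the plan says.** Section 4.1.1.2 gives the governing principle for adverse events: "all AEs will be considered as treatment-emergent unless the opposite can be clearly stated". It adds: "Imputation will be done only in the context of identifying TEAEs".

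Section 4.1.1.3 gives the rules for putting this into practice. For a completely missing start date the date of first dose is used, with an exception: "unless the end date suggests it could have started prior to this in which case impute the 1st January of the same year". The year meant is that of the end date. The only check on the result is to "ensure that the new imputed date is sensible i.e., is prior to the end date of the AE or medication". The imputed start is not checked against first dose or informed consent.

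Under Section 3.6.1, an event with onset at or after first dose is a TEAE, and so is an earlier event that increases in severity from first dose onwards. A pre-dose event that does not worsen "will be included in the data listings but will not be included in the AE summary tables". Section 4.2.6.1 builds the summary tables from TEAEs unless otherwise specified, and several of them are split "By periods as defined in section 3.1.6".

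**The concern.** The two sections set different burdens of proof. Section 4.1.1.2 needs clear evidence before an event is taken out of the treatment-emergent class. Section 4.1.1.3 needs only a suggestion that the event could have begun earlier. With an unknown start, nearly every end date on or after first dose allows an earlier onset, so on a literal reading the first-dose default survives mainly for events that have no end date either.

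The replacement date adds a second problem. It is tied to the year of the end date, not the year of first dose. Whether the event counts then depends on whether New Year falls between first dose and the end of the event, which has no clinical meaning.

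At stake is the completeness of the TEAE summaries. For events ending on or after first dose, the exception can only remove TEAEs compared with the first-dose default; it can never add one.

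A smaller gap concerns the by-period tables. They need an onset date to separate on-treatment from post-treatment events, but Section 4.1.1.2 ties imputation to the TEAE flag and no rule says how a partly dated event gets its period.

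**Working it through.** **Inputs.** The rule and its exception are in Section 4.1.1.3, and the TEAE definition is in Section 3.6.1. Section 1.2 gives a screening period of up to 45 days and 12 + 24 = 36 weeks from first dose to the end of follow-up, which is 252 days. The SAP states no figure on this point, so there is none to reproduce.

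**Step 1: apply the exception literally** (imputed start = 1 January of the end-date year; example dates are illustrative).

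| First dose | End date | Imputed start | Status |
|---|---|---|---|
| 15 Mar 2022 | 20 Apr 2022 | 1 Jan 2022 | pre-dose; not a TEAE unless it worsens |
| 15 Mar 2022 | 20 Oct 2022 | 1 Jan 2022 | pre-dose; not a TEAE unless it worsens |
| 15 Nov 2021 | 10 Dec 2021 | 1 Jan 2021 | pre-dose; not a TEAE unless it worsens |
| 15 Nov 2021 | 10 Jan 2022 | 1 Jan 2022 | after first dose; TEAE |
| 15 Mar 2022 | 1 Mar 2022 | 1 Jan 2022 | pre-dose; correct, the event ended before dosing |

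The first three rows show the conflict with Section 4.1.1.2: nothing in those dates clearly shows a pre-treatment event. In each of them the imputed start also lies more than 45 days before first dose, although Section 3.6.1 collects events only from screening. The fourth row shows the exception failing its own purpose. The last row is the case in which it works.

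**Step 2: how often the literal rule gives a pre-dose start.** Assume first-dose dates spread evenly over a 365-day year. An event ending t days after first dose gets a pre-dose start when both dates lie in the same year and first dose is not on 1 January. The share is (364 − t)/365. Averaging over end dates from day 0 to day T after first dose gives (364 − T/2)/365:

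- T = 84: (364 − 42)/365 = 322/365 = 0.882
- T = 252: (364 − 126)/365 = 238/365 = 0.652

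Direct enumeration of all date pairs gives the same 88% and 65%. The other 12% and 35% are dated on or after first dose and remain TEAEs.

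**Step 3: compare with the neighbouring rules in Section 4.1.1.3.** If only the start year is known and it is the first-dose year, the event is dated to first dose and is a TEAE. If nothing is known about the start and the end date lies in that same year, the event can be dated 1 January and not be a TEAE. Less information thus leads to the less conservative class. For a missing day with onset before first dose, the section uses the date of informed consent, not 1 January.

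**Step 4: period assignment.** Section 3.1.6 divides on-treatment from post-treatment at 14/15 days after the last dose. TEAE status cannot place an event on either side of that line. Section 3.1.6 has a default for a Day 1 assessment without a time, but none for an event with an incomplete onset date.

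**The case against.** The strongest reply is that the exception was meant only for events that ended before first dose. Section 4.1.1.3 presents its rules as the practical form of the principle in Section 4.1.1.2, and a reading that nearly empties the main rule is an unlikely intention. For such events a first-dose start would fall after the end date and breach the section's own check. On this reading 1 January of the end-date year is never later than the end date, so it is always pre-dose. The status is then right every time and the New Year effect disappears.

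That may well be what was meant, but it is not what is written. An end date before first dose proves an earlier start; it does not merely suggest that one was possible. The same section also names the first dose date explicitly as the cut-off in its end-date rule, and could have done so here. A programmer could follow the literal text in good faith.

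Three limits on the point do stand. Events that worsen after dosing remain TEAEs. Original dates stay in the listings, so no event disappears from the report. The period gap is inferred from the word limiting imputation to TEAEs: the SAP does not bar the use of imputed dates for period assignment and nowhere says that partly dated events are dropped.

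**Conclusion.** The wording of the exception conflicts with the stated default and should be corrected. The point is minor. Each affected event can change class completely, but the SAP gives no count of events with a wholly missing start date, and there are probably few. The 88% and 65% are shares of such events under the literal reading and evenly spread dates; they are not shares of all adverse events.

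A reader might infer that every undated event caught by the exception is moved before dosing. It is not: an end date in a later calendar year than first dose gives a start after dosing, and worsening keeps a pre-dose event in the tables. A reader might also infer that partly dated events are lost from the by-period tables. The SAP does not say so; it only leaves their assignment unstated. Nor does the text show that the trial's TEAE totals would be materially wrong.

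**What to change.** In Section 4.1.1.3, replace the rule for a completely missing start date with wording such as: *If the start date is wholly unknown, use the date of first dose. Only where the end date falls before first dose, use 1 January of the year in which the event or medication ended.* For adverse events, the later of that 1 January and the informed consent date may be used, provided that it is not after the end date. Medications should keep 1 January, because the rule covers them too and one that stopped before consent would otherwise get a start after its end.

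As a secondary clarification, state in Section 4.1.1.2 that imputed adverse event start dates also assign events to the Section 3.1.6 periods for the by-period tables in Section 4.2.6.1.

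The cost is two sentences and a small programming change. The consequence to accept is that a few events that really began before dosing may be counted as treatment-emergent, which is the direction Section 4.1.1.2 already chooses.

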## 1.2 Study design

This is a Phase IIb, multicentre, multinational, randomised, double-blind, placebo-controlled, dose-response study of MEDI7352 in participants 18 to 80 years of age (inclusive) with moderate-to-severe chronic pain of the knee during the previous 3 months or longer, caused by osteoarthritis (OA), not adequately controlled by standard-of-care treatments. See Figure 1 for an overview of the study design. See CSP Table 1 for the schedule of activities planned, including details on the study period.

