**Figure 1 Study design**

DSIS, daily sleep interference scores; EOT, end of treatment; IP, investigational product; NRS, numerical rating scale; Q2W, every 2 weeks; CCI

The screening period is up to 45 days; one rescreening attempt is allowed. Pain medication washout is at least 48 hours or 5 half-lives, whichever is longer, prior to the start of the numerical rating scale (NRS) pain score baseline period on Day -7. The baseline NRS pain score period comprises the scores from Day -7 to Day -1 (inclusive).

Visit 3 (Day 7), Visit 9 (Day 74) and Visit 10 (Day 77) may be performed at the participant's home by a qualified health care provider. Visits 9 and 10 cannot be on the same day.

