  - The number (%) of participants with any medical/surgical history (records) will be tabulated by MedDRA system organ class (SOC) and PT. A participant will only be counted once within a particular SOC/PT, regardless of multiple conditions/diseases/surgeries in the same SOC/PT. SOC and PT will be presented in alphabetical order.
- All prior/concomitant medications will be coded using the latest World Health Organization (WHO) Drug Global B3-format dictionary.

Summary tables of allowed and prohibited concomitant medications will present the number (%) of participants, using at least one medication by generic term within anatomical therapeutic chemical (ATC) classification. Participants will be counted once at each level of summarisation (ATC classification/generic term).

- OA related medical history, as collected in the OA medical history eCRF form, namely:
  - Duration of OA (years)
    - Calculated as: Randomization date - OA start date (collected on the OA medical history form), presented in years.
  - Duration of target knee pain (years)

- Calculated as: Randomization date - target knee pain start date (collected on the OA medical history form), presented in years.
- Target knee (left/right), n (%)
  - As collected on the OA medical history form.
- Baseline KL grade
  - As reported by Bioclinica
- Baseline pain intensity score (NRS)
  - As collected in the eDiary

In addition, disease-related treatment at screening will be summarised and will include:

- Previous/ongoing treatments
  - Nonsteroidal anti-inflammatory drugs (NSAIDs)/cyclooxygenase-2 (COX-2) inhibitors
  - Paracetamol
  - Opioids

Pain relief history evaluated in terms of:

- Not effective
- Intolerability
- Contraindication
- No access to opioids (only for opioids)
- Unwillingness to take opioids (only for opioids)

The number (%) of participants will be presented.

- Rescue medication variables defined in section 3.5.1.7 will be summarised by periods as defined in section 3.1.6.

Demographic and baseline characteristics data will also be listed.

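### Read literally, the partial-date rule borrowed for OA onset replaces a known month and year with the consent date and gives an OA duration below the entry minimum

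*SAP*

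**What the plan says.** SAP Section 4.1.1.3 gives these rules for partial start dates of adverse events and medications:

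- Day missing: "Missing day: Impute the 1st of the month unless month is same as month of first dose of study drug then impute first dose date". The next sentence adds "If the onset is before the first dose of study drug then impute with date of informed consent".
- Day and month missing: "impute 1st January unless year is the same as first dose date then impute first dose date".
- A general check on imputed start dates: "ensure that the new imputed date is sensible i.e., is prior to the end date of the AE or medication".

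The section then extends these rules to OA: "The same logic presented above will be used to impute partial dates of the start of the OA". That sentence ends by saying that the purpose is to derive OA duration from whichever parts of the date are available. It names no branch of the rules as inapplicable.

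Section 4.2.8 lists duration of OA among the baseline summaries: "Calculated as: Randomization date - OA start date (collected on the OA medical history form), presented in years".

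Two statements about the design bear on the result. Section 1.2 describes participants with "moderate-to-severe chronic pain of the knee during the previous 3 months or longer", caused by OA. The notes to Figure 1 say "The screening period is up to 45 days; one rescreening attempt is allowed".

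**The concern.** The consent-date sentence makes sense for adverse events. They are collected from screening onwards, so an event before first dose cannot lie far from consent. OA onset is different: it precedes first dose in every eligible participant, often by years. Applied to OA as written, the sentence covers every onset whose day is missing, and it discards a recorded month and year.

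The check on imputed dates does not catch this, because it compares with the end date of an adverse event or medication and OA onset has neither.

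At stake is the accuracy of one tabulated baseline characteristic. The affected values would all err in the same direction, towards recent onset.

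**Working it through.** The SAP states no figure for OA duration, so there is none to reproduce. The check is date arithmetic on its own rules.

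**Inputs**

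- Duration = (randomisation date − OA start date) / 365.25 (Section 4.2.8; year conversion in Section 4.1.1.3).
- Randomisation on Day 1 (Section 1.2); screening up to 45 days (notes to Figure 1).
- Minimum duration of OA knee pain: 3 months (Section 1.2), at 30.4573 days per month (Section 4.1.1.3).
- Assumed for illustration: randomisation on 15 March 2022.

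**1. Longest duration when onset is set to consent**

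- One full screening period: 45 / 365.25 = 0.123 years.
- Consent 28 days before randomisation: 28 / 365.25 = 0.077 years.
- Consent 7 days before randomisation: 7 / 365.25 = 0.019 years.

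**2. Shortest duration consistent with entry**

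- 3 × 30.4573 = 91.4 days; 91.4 / 365.25 = 0.250 years.

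Every value in step 1 is below this. If a rescreened participant kept the first consent date and had two full screening periods back to back (an assumption), the result would be 90 / 365.25 = 0.246 years, still below. Only a gap between the two screenings, with the first consent date retained, could exceed the minimum.

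**3. Same onset, different completeness**

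| Recorded onset | Literal rule sets onset to | Duration (years) |
|---|---|---|
| June 2012 | consent date | at most 0.12 |
| 2012 only | 1 January 2012 | 10.20 |
| June 2012, using the recorded month and year | 1 June 2012 | 9.79 |

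The more complete date gives the worse answer.

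**4. Year-only onset in the year of first dose**

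The rule substitutes the first-dose date. First dose and randomisation are both planned for Day 1, so duration is about 0. This can arise only when first dose falls at least about three months into the year, and in that case 1 January would satisfy the 3-month minimum.

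**5. Where the variable is used**

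The ANCOVA underlying MCP-Mod and the pairwise comparisons has dose, baseline score and KL grade as terms (Section 4.2.1.2.1.1). OA duration is not among them, and Section 4.2.8 plans no testing of baseline characteristics.

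**The case against.** The best reply is that the consent-date sentence was never meant this way. It follows directly on the exception for onsets in the month of first dose, and can be read as completing it: if the month matches but onset is known to precede dosing, use consent instead of the first-dose date. On that reading an eligible participant's OA onset, at least three months earlier, never reaches the consent branch, and June 2012 becomes 1 June 2012. The closing words about available date parts point the same way, as does the next bullet, which keeps a known year.

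This reply has force. It shows that a sensible intention is plausible and that one cannot be sure the programmed result will be wrong. It does not remove the defect, because the text does not limit the sentence to the month of first dose. On the literal reading, the instruction to reuse the same logic conflicts with the instruction to use the available parts. The reply also leaves the year-only case in the year of first dose untouched.

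A reader might also infer that a completely missing OA onset will be set to first dose, with zero duration. That is doubtful: the OA sentence speaks of partial dates, although the list it borrows from is also headed as partial dates and yet includes a completely missing case. The point here does not rely on it.

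**Conclusion.** The rule is wrong as written, at the lowest level of importance. Taken literally, a day-missing OA onset yields at most about 0.12 years within one screening period, against a minimum of 0.25 years. A year-only onset in the year of first dose yields about zero. The first result depends on the literal reading of the consent-date sentence; the second does not.

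A reader might go on to infer a percentage bias in mean OA duration. The SAP does not say how many onset dates lack a day, or whether those participants resemble the rest. If the share is p and missingness is unrelated to duration, the mean falls by roughly that same share, but this only restates the assumption. No bias figure can be given.

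Nor do the documents support any effect on efficacy conclusions, since OA duration enters no efficacy model. The original incomplete dates stay in the listings, so an affected value could be recognised and corrected.

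**What to change.** In Section 4.1.1.3, replace the sentence extending the adverse-event logic with a rule specific to OA start:

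- the consent-date and first-dose-date branches do not apply;
- day missing: first of the recorded month;
- day and month missing: 1 January of the recorded year;
- year missing: not imputed, and duration left missing.

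The same section already uses these date-part conventions for partial death dates, so nothing new is introduced. The first-of-month rule overstates duration by at most 30 days (30 / 365.25 = 0.08 years), and the 1 January rule by less than a year.

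The cost is about two lines of SAP text and a small change to one derivation. No other analysis needs to change.
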